6.5.11 Other Restrictions and Instructions for Trial Subjects

The subjects will be instructed to avoid changes in their general life style, such as diet, exercise and sleep habits, during the trial.

Intake of probiotic products as well as food and dietary supplements containing probiotics are not allowed from the screening visit and until the end of the final intervention period. Subjects will not be withdrawn from the trial due to single violations, but violations will be recorded as protocol deviations.

Any use of illicit drugs (euphorics or stimulants, such as cannabis and opium) is prohibited during the trial.

During the trial, subjects will be asked to:

- Refrain from consuming any food products that may contain live microbes (i.e. fermented milk products)
- Refrain from taking any non-steroidal anti-inflammatory drugs (NSAIDs)
- Refrain from participating in other clinical trials

For the two days prior to Visit 2, 3, 4 and 5, subjects will also be asked to:

- Refrain from alcohol and any nicotine products
- Refrain from consuming spicy food
- Refrain from consuming caffeine
- Avoid strenuous exercise

Subjects will also be asked to fast for 6 hours before attending Visit 2,3,4 and 5.

6.6 Assessments and Schedule of Measurements

6.6.1 Gastroscopy procedure incl. clinical scoring

A gastroscopy is a procedure where a thin, flexible tube called an endoscope is used to look inside the oesophagus, stomach and first part of the small intestine (duodenum). The gastroscopy procedure is expected to take less than 30 minutes including clinical scoring, sampling of biopsies and collecting luminal fluid.

During the procedure, a clinical evaluation of both the ventricle and the duodenum will be performed using the 5-point Lanza scale described previously¹³. In short, the gastroenterologist will enumerate mucosal hemorrhages, erosions, and ulcers for the ventricle and for the duodenum separately using the following 5-point Lanza scale:

0=normal stomach or duodenum

1=mucosal hemorrhages only

2=1 or 2 erosions observed

3=numerous (3–10) areas of erosion

4=large number of erosions (>10) and/or ulcer(s).

Erosion will be defined as a lesion producing a definite discontinuance in the mucosa but having no depth. Ulcer will be defined as any lesion of unequivocal depth at least 3 mm in diameter. The same gastroenterologist will perform all gastroscopies and perform all the clinical scoring, while remaining blinded for treatment arm.

6.6.2 Assessment of Safety

In Europe, strains of *Bifidobacterium* belonging to the specie *breve* have been granted QPS status by EFSA. This means that the strain used in this trial is considered safe to use in food and as a dietary supplement (EFSA, 2013). Bif195 has also been used in 3 previous (plus one ongoing) Chr Hansen-sponsored human clinical trials without any Adverse events (AEs) associated to trial product being reported.

The ASA challenge period of 4 weeks and the ASA dose of 300 mg can lead to some degree of discomfort for the subjects, but this is within the dose range clinically recommended and considered safe for chronic, daily use of ASA.

Subjects can always withdraw from the trial. Symptoms arising from ASA use is usually normalised within a few days. Subjects will also have access to call a medical doctor dedicated to this trial at any time, also in between trial visits. Also, the below safety assessments will be applicable for this trial:

Adverse Events

AEs will be recorded from Visit 2 until the end of the trial at Visit 5. Subjects will be asked during all visits to site to report any AEs experienced throughout the trial. AEs will be recorded and assessed as described in detail in protocol Section 7.10.

Pregnancy test

Women of childbearing potential will have a urinary pregnancy test performed using instant urine stick test at the screening visit (Visit 1).

Medical history

Relevant medical history such as chronic conditions and diseases or major surgery will be recorded at Visit 1. Smoking history and habits will also be recorded.

Physical examination

A short physical examination including auscultation of heart, lungs and blood pressure will be performed by a medical doctor at Visit 1.

Concomitant medication

Use of concomitant medication one year prior to the screening visit as well as herbal and dietary supplements will be registered on the appropriate page in the CRF until the end of the trial. Trial personnel will ask subjects at all trial visits about medication used.

Phone visits

On the fourth day after each gastroscopy (Visit 2,3,4 and 5), a phone visit will be conducted where trial staff will contact the subject and ensure the well-being of the subjects and at the same time remind the subject to start intake of ASA and trial product (the latter for phone visit 1 and 3 only).

Blood sampling

A non-fasting blood sample will be collected from all participants at all 5 visits for safety reasons and in order to detect any unknown condition that may compromise a participant's eligibility for the study. The parameters include creatinine, potassium, sodium, haemoglobin, haematocrit, red blood cells, HbA1c, alanine aminotransferase, aspartate transaminase, INR, leucocytes, thrombocytes and CRP.

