5.2 Assessment of Anticipated Benefits and Risks

The ASA intervention planned for this trial is designed (in length and daily dose) to create only a mild degree of deterioration of small intestinal mucosa tissue in healthy volunteers in the form of villous edema and ulcers, as we have observed with similar ASA dosing in a previous trial¹¹. This may create a mild degree of GI discomfort and symptoms for subjects during the trial. However, this is quickly reversed upon cessation of daily ASA use and the daily dose of ASA of 300 mg used in this trial is within the dose range recommended for chronic use of ASA for CVD protective reasons.

There are no known risks with administration of probiotics unless the trial population consists of severely ill or immunocompromised patients. In Europe, certain species of *Bifidobacteria* have been granted Qualified Presumption of Safety (QPS) status by the European Food Safety Authority (EFSA), including the *Bifidobacterium breve* to which the strain Bif195 belongs. This means that Bif195 is considered safe to use in food and as a dietary supplement (EFSA, 2013). Therefore, there are no known or expected risks or side effects for either the test or the placebo products used in this trial, but the risk of side effects cannot be excluded. Side effects, if any, are however expected to be minor and transient in nature. Side effects could typically be symptoms of digestive discomfort (abdominal discomfort, bloating, flatulence/passage of gas, borborygmi/rumbling stomach). With more than 4600 days of human exposure to the Bif195 strain in their clinical program, the sponsor Chr Hansen has not observed any adverse events assumed related to Bif195 intake.

A gastroscopy is a very safe and common procedure. Rare complications include bleeding, infections, perforation and reaction to sedation.

There are no direct benefits to the subjects for participation in this trial. The subjects, while being in the active arm with Bif195 co-administration might experience a reversal or dampening of the very mild GI symptoms induced by the ASA intervention described above.

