Phone visit			P1		P2			P3		P4
Day (visit window)	-14 (+5/-14)	0	4	31 (±1)	35 (±1)	6 weeks (+7)	0	4	31(±1)	35 (±1)
Phone call			X		X			X		X
Written informed consent	X									
Check of inclusion/exclusion criteria	X									
Urine pregnancy test (women only)	X									
Medical history	X									
Routine physical examination incl. blood pressure	X									
Demography	X									
Alcohol consumption	X									
Concomitant medication	X	X		X			X		X	
Height	X									
Body weight	X	X		X			X		X	
Randomisation		X								
Overnight fasting before visit		X		X			X		X	
Blood safety panel	X	X		X			X		X	
Other blood sampling		X		X			X		X	
Gastroscopy Incl. biopsies		X		X			X		X	
Hand-out of ASA		X					X			
Hand-out of trial product		X					X			
ASA accountability				X					X	
Trial product accountability				X					X	
Adverse events		X		X			X		X	

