6.10 Procedures for Handling Adverse Events

Adverse events (AEs) will be collected from Visit 2, the day before start of intervention with ASA and the trial product and through the end of the trial (Visit 5).

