6.10.2 Eliciting, Recording and Follow-up of Adverse Events

The subject will be asked if he/she has noticed any unfavourable effects when taking the investigational product. If the subject has noticed any unfavourable effects, an AE form in the CRF will be filled in for each separate AE. The form will cover onset, end, intensity, causality, action taken and outcome of the AE.

The subject must be followed-up by any clinical or biological examination considered as necessary by the medical judgment of the Investigator, until the abnormal condition is resolved, or the Investigator deems further observations or examinations to be no longer medically indicated.

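### AE recording ends at Visit 5, the day of the last gastroscopy and biopsies, although a phone visit is scheduled four days later

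*Protocol*

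**What the plan says.** **Recording window.** Protocol Section 6.6.2: "AEs will be recorded from Visit 2 until the end of the trial at Visit 5". Section 6.10 collects AEs from Visit 2, described as "the day before start of intervention with ASA and the trial product and through the end of the trial (Visit 5"), so the end is the same.

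**Where AEs are asked for.** Section 6.6.2: "Subjects will be asked during all visits to site to report any AEs experienced throughout the trial". In Table 1 the row "Adverse events" has four marks, in the same columns as the gastroscopy row (Visits 2 to 5) and none in the phone-visit columns. Section 6.6.4 likewise lists AE recording under Visits 2 to 5 only.

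**Contact after the last procedure.** Section 6.6.2: "On the fourth day after each gastroscopy (Visit 2,3,4 and 5), a phone visit will be conducted". Its stated purpose is to check on the subject and, for the first and third calls, to remind the subject to start intake. Table 1 puts Visit 5 at day 31 (±1) and P4 at day 35 (±1).

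**Closure.** Section 6.6.4 has the CRF termination form completed at Visit 5.

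**Risk named by the protocol.** Section 5.2 says of gastroscopy: "Rare complications include bleeding, infections, perforation and reaction to sedation".

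**Elicitation wording.** Section 6.10.2: "The subject will be asked if he/she has noticed any unfavourable effects when taking the investigational product".

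**The concern.** The last day on which AEs are recorded is also the day of an invasive procedure in healthy volunteers who have no direct benefit from the trial. A complaint that starts after the subject leaves Visit 5 falls outside the recording window. The protocol itself treats the days after biopsies as relevant: Section 6.5.7 leaves three days for the mucosa to heal before intake begins, and a call is scheduled after every gastroscopy, including the last. The protocol also declares the trial over at Visit 5 while planning a trial contact after it.

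At stake is the completeness of the safety record for the last procedure, and for the first days after the second ASA course. The efficacy analysis is not involved.

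**Working it through.** The plan gives no figure on this point to reproduce. The check is schedule arithmetic and a comparison of sections.

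**Inputs**
- Biopsies per gastroscopy: 6 duodenal and 2 ventricular (Section 6.2).
- Gastroscopies per completer: 4, at Visits 2 to 5 (Section 6.2).
- First dose in each period: 4th day after Visit 2 or Visit 4; course of 28 days (Section 6.5.7).
- Visit 5 at day 31 (±1), P4 at day 35 (±1) (Table 1).
- 25 randomised, 20 planned completers (Section 6.9.8).

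**Last dose against end of recording.** Last dose day = 4 + 28 − 1 = 31, the nominal day of Visit 5. Nominal AE follow-up after the last dose = 31 − 31 = 0 days.

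**Visit 5 to P4.** 35 − 31 = 4 days. If both windows are taken independently around the nominal days, the range is 34 − 32 = 2 to 36 − 30 = 6 days.

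**Gastroscopies with no later AE contact**

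| Subjects reaching Visit 5 | All gastroscopies | With no later AE contact | Share | Biopsies at Visit 5 |
|---|---|---|---|---|
| 20 (planned completers) | 4 × 20 = 80 | 20 | 25% | 8 × 20 = 160 |
| 25 (ceiling, no drop-out) | 4 × 25 = 100 | 25 | 25% | 8 × 25 = 200 |

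**Does another section close the gap?**
- Visits 3, 4 and 5 follow the first three gastroscopies, and the question in 6.6.2 is open, so those three are covered. No site visit follows Visit 5.
- Sections 6.10.2 and 6.10.7 require follow-up of an AE once it is known. They do not solicit new ones.
- Section 6.10.6 requires SAEs to be reported within 24 hours of awareness and gives no end date. Serious events that the site learns of after Visit 5 can still be reported.
- Section 6.6.2 lets subjects call a trial doctor at any time. That relies on spontaneous reports.
- The SAP's safety outcomes are blood parameters (Sections 1.2 and 5.5), with Visit 5 as the last sampling. It plans no AE analysis.

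What remains uncovered is systematic collection of new events after Visit 5, mainly non-serious ones.

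**The case against.** The strongest reply is that little is lost in practice. A bleed or perforation needing admission, or judged medically important, is an SAE under Section 6.10.5, and SAE reporting has no cut-off. P4 gives staff a way to hear of it, as does the doctor's telephone line. AEs open at Visit 5 are still followed. Section 6.9.1 allows the CRF of a subject who leaves to be completed shortly after the final visit. Complications are described as rare, and no rate is given. All of this stands and limits the point to events that nobody is instructed to ask about or record. It does not remove it, because the call meant to find problems has no AE entry.

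A reader might also infer more than the documents support:

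- **That the wash-out and the days after earlier biopsies go unasked.** Section 6.10.2 alone could be read that way, but the question in 6.6.2 covers the whole trial up to each site visit, and Section 6.10.1 defines AEs regardless of relation to treatment. The two wordings are inconsistent; together they do not exclude those days.
- **That unequal windows bias the comparison.** Visit 2 to Visit 4 is about 31 + 42 = 73 days and Visit 4 to Visit 5 is 31. The extra 42 days are off ASA and off product, order is randomised 1:1, and the SAP compares no AE counts by period or treatment. Recording through P4 would give 73 against 35 days, so equal windows are not the reason for the change.
- **That serious complications would go unreported.** The SAE rule does not say so.

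**Conclusion.** The point holds in limited form. AE recording ends on the day of the fourth gastroscopy, nominally with no follow-up after the last dose of ASA and product, and the later phone visit is not used for AE recording. New events after Visit 5 are not systematically collected after one in four gastroscopies per completer: 20 of 80, or 160 biopsies, if the planned 20 complete. The 25 of 100 (200 biopsies) is a ceiling that assumes no drop-out.

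These are counts of procedures without later AE collection, not of missed events. The documents give no complication rate from which to estimate those. The conclusion rests on Table 1 as extracted (its layout is partly broken, but its AE marks agree with Section 6.6.4) and on the absence of any written instruction for P4. Staff might note a complaint at that call, but the protocol does not provide for it.

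This is a modest gap in safety collection that is worth closing because the remedy is nearly free. It does not call the efficacy results into question.

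**What to change.** 1. In Sections 6.6.2 and 6.10, extend AE recording through phone visit P4. Reconcile the statement that the trial ends at Visit 5 with the scheduling of P4.
2. In Table 1, add an AE entry at P4.
3. In Section 6.6.4, complete the CRF termination form after P4 instead of at Visit 5.
4. Align the question in Section 6.10.2 with the open question already in 6.6.2, so that it is not tied to the time of product intake.
5. While editing 6.10, reconcile its placing of Visit 2 on the day before intervention starts with the 4th-day start in 6.5.7.

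Cost: protocol and CRF wording, a few minutes of recording on a call that already takes place, and a CRF that closes about four days later per subject. No new visit, procedure or sample is needed.

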6.4.2 Exclusion Criteria

For a subject to be eligible for the trial, all the below criteria must be checked with a “no”:

- Abdominal surgery which, as judged by the Investigator, might affect the GI function (except appendectomy and cholecystectomy)
- History of peptic ulcer disease
- Known history of *Helicobacter Pylori* infection
- Any known bleeding disorder
- Allergy to ASA
- Resting diastolic blood pressure ≥ 95 mmHg
- Resting systolic blood pressure ≥ 150 mmHg
- A current diagnosis of psychiatric disease

- Systemic use of antibiotics, steroids (except contraceptives) or antimicrobial medication in the last month
- Daily usage of non-steroidal anti-inflammatory drugs in the last 2 months or incidental use in the last 2 weeks prior to screening (ASA, Ibuprofen, Diclofenac, Naproxen, Celecoxib, Mefenamic acid, Etoricoxib, Indometacin)
- Usage of medications, except contraceptives, in the last 2 weeks prior to screening
- Regular use of probiotics in the last month
- Use of laxatives, anti-diarrheals, anti-cholinergics and proton pump inhibitors within last 2 months prior to screening
- Use of immunosuppressant drugs within last 4 weeks prior to screening
- Diagnosed inflammatory gastrointestinal disease and/or irritable bowel syndrome
- Any other disease that, by the Investigators discretion, could interfere with the intestinal barrier function of the subject
- Participation in other clinical trials in the past 2 months prior to screening
- Smoking and/or frequent use of other nicotine products
- Higher alcohol intake than what the board of Health recommends
- Desire and/or plans to change current diet and/or exercise regime during the participation of this trial
- For Women: Pregnancy or lactation

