6.4.3 Subject Withdrawal Criteria

Participation in the trial is voluntary, and subjects have the right to withdraw from the trial at any time without providing a reason, and with no loss of benefits to which the subject is otherwise entitled. If a trial subject chooses to withdraw, the trial personnel must be informed immediately, and every effort should be made to complete the end-of-trial assessments and document the reason for discontinuation in the case report form (CRF). The Sponsor should be notified as soon as possible about any discontinued subjects.

Any subject who prematurely terminates participation and who has consumed the test or reference product at least once will be asked to undergo a final examination (end-of-trial visit/early termination visit). For subjects considered lost to follow-up, the CRF will be completed up to the last visit.

The Investigator has the right to terminate participation of any subject at any time if they deem it in the subject's best interest.

Examples of possible reasons for premature withdrawal of a trial subject include, but are not limited to:

- Subject withdraws consent for personal reasons
- Subject's general condition and/or data from the visit 2 gastroscopy procedure contraindicates continuing the trial, as judged by the trial personnel and/or the principal Investigator

- Participation in other clinical trials during participation of this trial
- Significant non-compliance with trial protocol or general lack of cooperation
- Pregnancy
- A serious adverse event (SAE)
- Lost to follow-up
- Any other reason as determined by the principal Investigator

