6.5.7 Administration of Trial Treatment for Each Subject

The subjects will consume one tablet of 300 mg ASA daily for 4 weeks, 28 days, in each trial period together with breakfast. If a subject forgets to consume a dose of ASA, it can be taken later on the same day, with or without a meal, but an additional dose should not be taken on the following day to compensate for a missing dose on the day before.

The subjects will consume 2 capsules of trial product (Bif195/active or placebo) daily during the 4 weeks, 28 days, treatment period. One of the capsules should be taken with the subject's breakfast, but preferably 10 minutes before intake of the ASA. The other capsule should be taken in the evening, with or without a meal.

In order to allow 3 days of healing of the mucosal wall after biopsies, the first administration of ASA and trial product will take place at breakfast on the 4th day after Visit 2 and again on the 4th day after visit 4.

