6.5.10 Prior and Concomitant Therapy

Any concomitant medication should be avoided during the entire duration of the trial, except contraceptives. All rescue medications taken during the trial period as well as dietary and herbal supplements will be registered on the appropriate page in the CRF. Use of concomitant medication and supplements during the last year and use of rescue medication from screening visit until end of trial should be documented.

The last 2 months prior to screening, or incidental use in the last 2 weeks prior to screening, and until final examination (Visit 5); all medications (including over-the-counter products and large doses of vitamins and/or mineral) that might have an effect on gut microbiota, gut regularity or gut symptoms, in particular NSAID (e.g. ibuprofen, ASA), laxative and intake of probiotics products are prohibited.

Use of systemic immunosuppressant drugs is not allowed for 4 weeks prior to the screening visit.

Antibiotics and steroids (except contraceptives) are prohibited from 2 months prior to the screening visit until the end of the trial. Subjects taking antibiotics during the trial will be discontinued from the trial.

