6.6.4 Description of Visits and Trial Periods

Visit 1, Screening Visit

At visit 1 the following procedures and assessments will be performed:

- Subjects will receive oral and written information about the trial and be allowed to ask any questions they may have
- Subjects will sign the informed consent document
- Inclusion and exclusion criteria will be checked
- Relevant medical history will be recorded
- Concomitant medication will be recorded
- Demographic data will be recorded
- A physical examination including auscultation of heart, blood pressure and lungs will be performed by a medical doctor and safety blood samples will be collected.
- A urine pregnancy test will be performed in all women of child-bearing potential.
- Height and weight will be recorded, and BMI calculated as kg/m². Weight will be recorded with the subject wearing only light clothing and without shoes
- Subjects will receive instruction on exclusion of specified probiotic products as well as food and dietary supplements containing probiotics for the duration of the run-in and intervention period and receive a list with prohibited products
- Subjects will be instructed not to change their habitual diet and life style (physical activity level, sleep habits) during the entire course of the trial
- Subjects will be instructed to fast for 6 hours before visit 2

Run-in Period

During the run-in period (2 weeks) and in between all visits, subjects will:

- Exclude probiotic products as well as food and dietary supplements containing probiotics from their diet
- Maintain their habitual diet and life style (physical activity level, sleep habits)
- Refrain from taking any NSAIDs or other medication

Before Visit 2-5, subjects will:

- Refrain from consuming alcohol, caffeine and spicy food for 48 hours prior to visit
- Avoid strenuous exercise 48 hours prior to visit
- Fast for 6 hours before attending the visit

Visit 2-5:

- Any adverse events will be recorded
- Concomitant medication will be recorded
- Body weight will be measured with subject in light clothing and without shoes

- Collection of blood samples will be performed
- Gastroscopy procedure including clinical scoring, mucosal biopsies and obtaining luminal fluid will be performed as previously described
- Subjects will be re-instructed on exclusion of prohibited food products and supplements that apply in the period leading up to the next visit
- The subject will be randomised (Visit 2 only)

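### Pregnancy is an exclusion, but the only scheduled test is at screening: 13 to 32 days before the first ASA dose and 85 to 113 days before the second course

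*Protocol*

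**What the plan says.** Protocol section 6.4.2 lists among the exclusions "For Women: Pregnancy or lactation". Section 6.4.3, under "Examples of possible reasons for premature withdrawal of a trial subject", gives pregnancy as a separate bullet.

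Three places set the timing of the test, and they agree:

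- Section 6.6.2: "Women of childbearing potential will have a urinary pregnancy test performed using instant urine stick test at the screening visit (Visit 1".
- Table 1 (section 6.2): the row "Urine pregnancy test (women only" has one mark, under Visit 1. The row for checking inclusion and exclusion criteria also has one mark, under Visit 1.
- Section 6.6.4, in the Visit 1 list: "A urine pregnancy test will be performed in all women of child-bearing potential". The list for Visits 2 to 5 has no pregnancy test.

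Randomisation is at Visit 2, and gastroscopy with biopsies is at Visits 2 to 5. Under section 6.5.7 the start of dosing with ASA and capsules "will take place at breakfast on the 4th day after Visit 2 and again on the 4th day after visit 4". On contraception, the relevant text is in section 6.5.10: "Any concomitant medication should be avoided during the entire duration of the trial, except contraceptives". This permits contraceptives without requiring them.

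**The concern.** A screening result shows that a woman was not detectably pregnant on that day. The protocol then relies on it for randomisation, four gastroscopies and two separate 28-day ASA courses, the second of which starts about three months later. A woman who conceives after Visit 1 can reach any of these steps while meeting the protocol's own exclusion, and nothing in the schedule would show it.

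The repeated safety blood draw shows that the protocol accepts eligibility-related testing after screening. Section 6.6.2 says a "blood sample will be collected from all participants at all 5 visits for safety reasons and in order to detect any unknown condition" that might affect eligibility. Its listed parameters, however, contain no pregnancy marker.

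The subjects are healthy volunteers aged 18 to 40, and section 5.2 says they gain no direct benefit. What is at stake is their safety. The argument does not rest on lost data, because a positive test at Visit 4 would still leave an incomplete crossover pair.

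**Working it through.** **Inputs from the protocol**

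- Visit 1: day -14, window +5/-14, so day -28 to day -9, which is 9 to 28 days before Visit 2 (Table 1).
- First ASA dose: day 4 after Visit 2 and day 4 after Visit 4 (section 6.5.7).
- Visit 3: day 31 ± 1, so day 30 to 32 (Table 1).
- Wash-out: 6 weeks (+7 days), so 42 to 49 days (Table 1), counted from Visit 3 to Visit 4 (section 6.4).

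**Check of the timeline against the plan's own figure.** Nominal duration is 14 + 31 + 42 + 31 = 118 days, or 118/7 = 16.9 weeks. This matches the approximately 17 weeks in section 6.2.

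**Age of the only test at each step**

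- Randomisation (Visit 2): 9 to 28 days; nominal 14.
- First ASA dose: 9 + 4 = 13 to 28 + 4 = 32 days; nominal 14 + 4 = 18.
- Visit 4, counted from Visit 2: 30 + 42 = 72 to 32 + 49 = 81 days.
- First dose of the second course: 9 + 72 + 4 = 85 to 28 + 81 + 4 = 113 days; nominal 14 + 31 + 42 + 4 = 91.

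**Other readings of the schedule.** If the wash-out ran from the phone visit on day 35 ± 1, the last range would be 9 + 34 + 42 + 4 = 89 to 28 + 36 + 49 + 4 = 117 days. Section 6.10 describes Visit 2 as the day before intervention starts, which conflicts with the day-4 start; on that reading the two ranges are 10 to 29 and 82 to 110 days. Neither changes the conclusion.

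**Could another scheduled procedure detect a pregnancy?**

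- Safety blood panel (6.6.2): taken at all five visits; no hCG among the listed parameters.
- Adverse event questions (6.10.2): about unfavourable effects of the product; no pregnancy question specified.
- Phone visits (6.6.2): well-being and, at the first and third calls, a reminder to start intake; no pregnancy question specified.
- Withdrawal for pregnancy (6.4.3): takes effect only once the pregnancy is known.

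**Expected number.** The documents give neither the number of women nor their contraceptive use. Assume 12 women among 25 subjects and 1 to 10 pregnancies per 100 woman-years. Expected conceptions = women × annual rate × days/365.25.

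- Visit 1 to Visit 2 (the most a Visit 2 test could catch): 12 × 0.01 × 9/365.25 = 0.003 to 12 × 0.10 × 28/365.25 = 0.09.
- Visit 1 to the second ASA start: 12 × 0.01 × 85/365.25 = 0.03 to 12 × 0.10 × 113/365.25 = 0.37.

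**With tests at Visits 2 and 4**, the gap before each course falls to 4 days. The number of tests is 25 × 2 = 50 if every randomised subject were a woman, or 12 × 2 = 24 for 12 women.

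**The case against.** The schedule is internally consistent, and no passage sets a testing standard that it fails. The documents do not say what harm ASA or gastroscopy would do in pregnancy. This stands: the point is a gap, not a contradiction, and its weight comes only from the protocol's own decision to exclude pregnant women.

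The yield is small and rests on assumed inputs. That also stands. The 0.37 pairs the highest rate with the longest window and keeps all 12 women in the trial. Applying the planned 20% drop-out to the whole interval would give 0.37 × 0.8 = 0.30. It also counts very early pregnancies and conceptions in the 4 days after Visit 4, which the added tests would miss, and conceptions during the first course, where some exposure has already occurred. Self-report would lower it further.

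Partial safeguards exist. Staff phone each subject on the day ASA starts, a trial doctor can be reached at any time, and section 6.5.5 gives a randomisation number at Visit 2 only to suitable subjects. Yet none of these is a test, and suitability is not defined there. The subject information sheet and laboratory manual are not available to us. They might contain contraception advice or a request to report pregnancy, and the listed blood parameters may not be exhaustive. A repeat test, however, would be expected in Table 1, section 6.6.2 or section 6.6.4, and all three show Visit 1 only.

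**Conclusion.** The concern holds. As written, a woman who becomes pregnant after screening could be randomised, undergo gastroscopy and start either ASA course undetected unless she reports it herself. The intervals of 13 to 32 and 85 to 113 days follow from the protocol's windows and need no outside figure. Only the 0.03 to 0.37 expected conceptions rest on assumptions (12 women; 1 to 10 pregnancies per 100 woman-years), and that range is an upper view of what the added tests could catch. The larger gain is at Visit 4; the most a Visit 2 test could catch is 0.003 to 0.09. The trial's statistical conclusions are not affected. The change should be made because the risk, though small, falls on healthy volunteers and costs very little to reduce.

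**What to change.** Add a urine stick test for women of childbearing potential at two existing visits:

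- Visit 2, with the result known before gastroscopy and randomisation.
- Visit 4, with the result known before gastroscopy and the ASA hand-out marked there in Table 1.

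This needs two further marks in Table 1 and one sentence each in sections 6.6.2 and 6.6.4. The cost is two sticks per woman. Fifty sticks cover 25 randomised subjects even if all were women; replacing drop-outs, or testing someone at Visit 2 who is then not randomised, would add a few. No extra visit, staff or invasive procedure is needed.

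Alternatively, hCG could be added to the safety blood sample at Visits 2 and 4, which section 6.8.1 says is analysed in-house on the day of collection. Gastroscopy would then have to wait for the result. Under either option a very early pregnancy, or conception during a course, would still be missed.
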